- Subjects to complete 5-D itch scale (preferably first) and Skindex-10 scale. If the first visit of the week is missed, the subject may complete the worksheets at their next visit for the same week. The questionnaires could be completed before or during dialysis (preferably within 1 hour of the dialysis) but before dosing
- Patient Global Impression of Change
- AE assessment
- Concomitant medications (including antipruritic medications)

Note: The end-of-treatment visit in the double-blind period will be the first dialysis visit following the last dose of investigational product, i.e., first dialysis on Week 13/Day 85, which also corresponds to Day 1 of the open-label extension period.

8.6 Follow-up Period (ONLY for Subjects not Participating in the Open-label Extension Phase)/Day 85 to Day 95

- Pre-dialysis vital signs, including body temperature, heart rate, and blood pressure, will be recorded at the follow-up visit (at 7 to 10 days after end-of-treatment/early termination visit). Heart rate will be measured at each dialysis visit during the follow-up period; if heart rate is clinically significant at visits outside the follow-up visit, the heart rate will be recorded in the eCRF
- WI-NRS worksheets to be completed only on dialysis days
- AEs assessment
- Concomitant medications
- Structured safety evaluation: A list of specific signs/symptoms will be verified with the subject by qualified site study staff once during the follow-up period

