10.5.4 Clinical Laboratory Evaluations

Not every out-of-range laboratory result qualifies as an AE. A laboratory investigation result must be reported as an AE if it meets any of the following criteria:

- Is accompanied by clinical symptoms
- Results in a change in study treatment (e.g., dosage modification, treatment interruption, or treatment discontinuation)
- Results in a medical intervention (e.g., potassium supplementation for hypokalaemia) or a change in concomitant therapy
- Presents shift of a parameter from a normal value to a pathological value, or results in a deterioration of common toxicity criteria grade, or a further worsening of an already pathological value
- Is clinically significant in the Investigator’s judgement

It is the Investigator’s responsibility to review all laboratory findings. Medical and scientific judgement should be exercised in deciding whether an isolated laboratory abnormality should be classified as an AE. When evaluating such changes, the extent of deviation from the reference range, the duration until return to the reference range, either while continuing treatment or after the end of treatment with the investigational product,

and the range of variation of the respective parameter within its reference range, must be taken into consideration.

If, at the end of the treatment phase, there are pathological laboratory values which were not present at baseline, further clinical or laboratory investigations should be performed until the values return to within reference range or until a plausible explanation (e.g., concomitant disease) is found for the pathological laboratory values.

The Investigator should decide, based on the above criteria and the clinical condition of a subject, whether a change in a laboratory parameter is clinically significant and therefore represents an AE. If the Investigator considers such an AE as serious (e.g., medically significant event fulfilling criteria per Section 10.7.1), it must be reported as an SAE.

If a laboratory abnormality meeting the above criteria is a sign of a disease or syndrome only the diagnosis should be recorded in the eCRF.

If a laboratory abnormality meeting the above criteria is not a sign of a disease or syndrome, the abnormality itself should be recorded in the eCRF, along with a descriptor indicating if the test result is above or below the normal range (e.g., “elevated potassium,” as opposed to “abnormal potassium”).

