12.9.1 Adverse Events

All AEs and pre-treatment AEs will be coded using MedDRA to MedDRA SOC and PT for standardisation and summary purposes.

All reported AEs will be included in summary tables by treatment group and by study period, as appropriate. AEs will also be presented in by-subject AE listings.

AEs relative to the double-blind period are identified as any AE:

- With an onset date after the first dose of the investigational product in the double-blind period for subjects who do not enter the open-label extension period.
- With an onset date after the first dose of the investigational product in the double-blind period up to the first dose of difelikefalin in the open-label extension period for subjects who continue into the open-label extension period.

AEs relative to the open-label extension period are identified as any AE with an onset date after the first dose of difelikefalin in the open-label extension period.

A pre-treatment AE is defined as any AE that has an onset before the first investigational product administration.

The number and percentage of subjects experiencing AEs will be summarised by treatment group and by study period. A subject will be counted only once in the incidence count for a MedDRA SOC or PT, although a subject may have multiple occurrences (start and stop) of an event associated with a specific MedDRA SOC or PT.

The incidence and percentage of subjects experiencing treatment-emergent SAEs and AEs leading to investigational product discontinuation will be presented by the appropriate MedDRA SOC and PT.

AEs will also be summarised by severity and by relationship to investigational product for each study period. If the severity and/or relationship to the investigational product of an AE is missing, a worst-case scenario will be assumed (i.e., the AE will be categorised as “severe” and/or “related” to the investigational product). If a subject reports the same AE multiple times the event with the worst severity and the strongest relationship to investigational product will be tabulated.

For each study period, an overall summary table will be provided, presenting for each treatment group, the number and percentage of subjects as well as the number of events for AEs, SAEs, treatment-emergent deaths, treatment-related AEs, treatment-related SAEs, severe AEs, AEs leading to investigational product interruption, AEs leading to investigational product discontinuation and AESIs.

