2.2 Study Design

This is a Phase 3, multicentre, controlled, randomised study to evaluate the efficacy and safety of difelikefalin 0.5 µg/kg compared to placebo in reducing the intensity of itch in adult Chinese HD subjects with moderate-to-severe pruritus (see [Figure 1 - Study Schema](#) below).

The study includes a 12-week double-blind placebo-controlled treatment period and a 14-week optional open-label extension period. A 4-week period (including a 7-day run-in period during the week prior to randomisation) before entry into the double-blind period is defined as the screening period, during which subjects do not receive any investigational product.

During the open-label extension period, difelikefalin is administered for 14 weeks (3 times weekly), starting at Week 13 (or up to 1 week following the double-blind period). The first visit and first dosing for the open-label extension phase of the study occurs immediately on the day of the last visit of the double-blind period or up to 1 week after the end of the double-blind period. The participation in the open-label extension period is optional.

[figure not shown]
The study also includes a 1-week (1 week to 10 days) follow-up period after last administration of investigational product (end of double-blind period or end of open-label extension period or early discontinuation).

Throughout the study, subjects could continuously use any conditionally permitted concomitant medications (e.g., to treat symptoms of chronic renal failure or other comorbidities) used at the start of the screening period.

Refer to [Table 1 - Schedule of Events and Assessments for the Double-blind Period](#) and [Table 2 - Schedule of Events and Assessments for the Open-label Extension Period](#) for the frequency and timing of the required study assessments.

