- 2 Each visit during the double-blind period coincides with the subject's normal dialysis treatments.
- 3 The end-of-treatment visit in the double-blind phase is the first dialysis visit following the last dose of investigational product (i.e., first dialysis on Week 13 (Day 85)), which also corresponds to Day 1 of the first day of the open-label extension. For subjects not participating in the open-label extension, Day 85 corresponds to Day 1 of the follow-up period.
- 4 Medical history is to be updated on Day 1 with any changes since the screening visit, and inclusion/exclusion criteria are confirmed prior to randomisation. Antipruritic medication is to be updated at each dialysis visit during the run-in period.
- 5 12-lead ECG must be performed prior to the start of dialysis at screening, Day 85 (double-blind period end of treatment), or at early termination visit.
- 6 Pre-dialysis vital signs, including body temperature, heart rate, and blood pressure, are to be recorded on Days 1, 15, 29, 43, 57, 71 and 85 (double-blind period end of treatment), or at early termination visit only when the subject is in a sitting or semi-recumbent position. Heart rate is to be measured at each dialysis; if heart rate is clinically significant at visits outside the pre-specified visits per Schedule of Events, the heart rate is to be recorded in the eCRF.
- 7 Pre-dialysis vital signs, including body temperature, heart rate, and blood pressure, are to be recorded at the follow-up visit (at 7 to 10 days after EoT/ET visit). Heart rate is to be measured at each dialysis visit during the follow-up period; if heart rate is clinically significant at visits outside the follow-up visit, the heart rate is to be recorded in the eCRF.
- 8 Blood samples for clinical laboratory evaluation are to be taken at screening, and on Days 1 and 85 (double-blind period end of treatment), or at early termination visit only and are to be assessed at central laboratory. Haematology includes basophil %, basophil (absolute), eosinophil %, eosinophil (absolute), haematocrit, haemoglobin, lymphocyte %, lymphocyte (absolute), MCH, MCHC, MCV, monocyte %, monocyte (absolute), neutrophil %, neutrophil (absolute), platelet, RDW, red blood cells, white blood cells. Serum chemistry will include albumin, alkaline phosphatase, ALT/SGPT, AST/SGOT, bilirubin (total), BUN, calcium, chloride, creatinine, glucose, phosphorus, potassium, sodium.

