4.8.1 Adverse Events

AEs data are collected from the time the informed consent form (ICF) is signed by the subject. The AE reporting period ends at the last study contact. Missing dates/partial dates of AEs will be handled as per [Section 4.1.9](#).

AEs relative to the open-label extension period are identified as any AE with an onset date on or after the first dose of difelikefalin in the open-label extension period.

All tabular adverse event summaries will only include AEs relative to the open-label extension period.

An AE will be classified as related to study drug if the relationship to study drug was recorded as 'Certain' or 'Probable/Likely' or 'Possible' in eCRF, as determined by the investigator. An AE will be classified as unrelated to study drug if the relationship to study drug was recorded as 'Unlikely' or 'Unrelated' in eCRF as determined by the investigator.

An SAE is defined as an AE when "Is this AE considered as Serious?" on the "Adverse Event" eCRF page is "Yes".

An AE leading to investigational product interruption is defined as an AE where the action taken with study drug is "Drug Interrupted" on the "Adverse Event" eCRF page. An AE leading to investigational product discontinuation is defined as is defined as an AE where the action taken with study drug is "Drug Withdrawn" on the "Adverse Event" eCRF page. An AE leading to early study termination is defined as an AE where other action taken is "Early Study Termination".

Adverse Events of Special Interest (AESI)

An AESI is a medical occurrence specific to the product or program. Any AE with the following MedDRA PT is to be identified as an AESI:

- gait disturbance
- fall
- dizziness
- somnolence
- seizure
- syncope
- mental status changes
- mood altered
- feeling abnormal
- sinus tachycardia, tachycardia, and tachyarrhythmia
- palpitations

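### SAP 4.8.1's date-only rule puts findings from the pre-dose Day 85 assessments into the open-label AE tables for subjects who start open-label drug that day

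*SAP*

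**What the plan says.** SAP 4.8.1 defines the open-label events: "AEs relative to the open-label extension period are identified as any AE with an onset date on or after the first dose of difelikefalin", meaning the first extension dose. It restricts all AE summary tables to these events and uses neither an onset time nor a pre-dose/post-dose distinction.

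Protocol 12.9.1 draws the line differently. For subjects who continue, a double-blind AE is one "With an onset date after the first dose of the investigational product in the double-blind period up to the first dose of difelikefalin", again meaning the first extension dose. For the open-label period it says: "AEs relative to the open-label extension period are identified as any AE with an onset date after the first dose of difelikefalin", with the same meaning. SAP Section 1 gives the SAP precedence over the protocol and points to Section 1.2 for differences. Section 1.2 lists only the added 5-D itch and Skindex-10 responder analyses.

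On timing, Protocol 8.5 places the double-blind end-of-treatment visit at the "first dialysis on Week 13/Day 85, which also corresponds to Day 1 of the open-label extension period". SAP 2.2 allows some latitude: the first open-label visit and dose "occurs immediately on the day of the last visit of the double-blind period or up to 1 week after the end of the double-blind period".

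On what becomes an AE, Protocol 9.3 requires reporting of new or worsened ECG findings that the investigator judges clinically relevant. Protocol 10.5.4 gives as one criterion for a laboratory result "Presents shift of a parameter from a normal value to a pathological value". Protocol 10.5.6 covers clinically significant vital signs.

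**The concern.** For a subject who starts open-label drug on Day 85, that date has a pre-dose part and a post-dose part, and the SAP rule treats the whole date as open-label. The scheduled end-of-treatment testing lies in the pre-dose part. A finding from it reflects the double-blind treatment but is counted in the extension.

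This matters most in the Placebo/Difelikefalin column, the only group whose first exposure to the drug is in the extension. There, a finding made after placebo alone is tabulated among events on difelikefalin. The SAP is also inconsistent with itself: one Day 85 ECG or blood sample can be the pre-treatment baseline in the ECG or laboratory tables and the source of an on-treatment event in the AE tables. A misassigned event would also be missing from the SAP's listing of AEs that began in the double-blind period and led to discontinuation, early termination or death in the extension.

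**Working it through.** The plan states no figure on this point, so the check applies the rules to the Day 85 sequence and then counts the scheduled assessments exposed.

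**Order of events on Day 85, same-day starter.** ECG, vital signs, chemistry and haematology are taken before dialysis (Protocol 8.5; Table 1, footnotes 5, 6 and 8). Dialysis follows. Open-label drug is given within 15 minutes after dialysis ends (Protocol 8.7.1). The measurements therefore always precede the dose.

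**Period assigned under three rules.**

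| Event | SAP 4.8.1: onset date ≥ dose date | Protocol 12.9.1 read on dates: onset date > dose date | Onset time compared with dose time |
|---|---|---|---|
| Same-day starter, pre-dialysis finding dated Day 85 | open-label | double-blind | double-blind |
| Same-day starter, reaction after the dose on Day 85 | open-label | double-blind | open-label |
| Event on the next day | open-label | open-label | open-label |
| Day 85 finding, first open-label dose up to 1 week later | double-blind | double-blind | double-blind |

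The SAP rule gets the first row wrong. The protocol wording, read on dates, gets the second row wrong. Only a comparison with the dose time gets every row right.

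**Scheduled post-baseline double-blind assessments falling on Day 85** (Protocol Table 1 and footnotes):

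- ECG: Day 85 only, so 1 of 1.
- Full chemistry and haematology panel: Day 85 only, so 1 of 1.
- Vital signs: Days 15, 29, 43, 57, 71 and 85, so 1 of 6.
- Potassium: separate tests on Days 15, 29, 43, 57 and 71, plus the Day 85 chemistry, so 1 of 6.

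The extension itself schedules one ECG and one full panel, both at its end-of-treatment visit (Table 2). For a same-day starter who completes, 1 / (1 + 1) = one half of the scheduled ECGs and full panels dated within the SAP's open-label window are pre-dose.

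**Other AEs.** The switch day is 1 of 14 × 7 = 98 days of open-label treatment. Symptoms sought through the structured safety evaluation are not concentrated on it. That evaluation is weekly and is not to be done on Monday or Tuesday (Table 1, footnote 17). Day 85 is 84 = 12 × 7 days after Day 1, so it is the same weekday, preferably a Monday or Tuesday.

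**Sensitivity of the most-common-AE table (illustration only).** The threshold is 2% of subjects in any group. The documents do not give the number entering the extension. If a sequence has 101 to 129 subjects (129 is the planned enrolment per group), 0.02 × 101 = 2.02 and 0.02 × 129 = 2.58, so 3 subjects with one preferred term reach the threshold. With 51 to 100 subjects, 0.02 × 51 = 1.02 and 0.02 × 100 = 2, so 2 subjects do. This shows how few misassigned findings could alter that table. It does not predict that they will occur.

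**The case against.** The best defence of the SAP wording is that it keeps genuine reactions after the first open-label dose in the open-label tables. The protocol wording, read on dates, would send them to the double-blind period. In first-exposure subjects that would be the worse error. This stands, and it rules out simply restoring the protocol's wording.

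It is also fair that the rule errs towards over-counting on active drug and that the safety analyses are descriptive, so no test or decision depends on it. That limits the severity but does not make the classification right.

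Several further points limit the size, and they stand:

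- Only ECG findings judged clinically relevant must be reported. Protocol 10.5.4 also asks for judgement on isolated laboratory abnormalities and says the same abnormality is not recorded again at each visit.
- Where a diagnosis is established, Protocol 10.5.2 dates it from the first symptom.
- The documents do not say how onset is dated for central-laboratory findings.
- Five of the six post-baseline potassium tests fall before Day 85, so the full-panel count overstates the exposure for potassium.
- SAP 4.1.9 refers to AE times as well as dates, so onset times may exist. Section 4.8.1 does not use them.

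Three stronger readings are tempting. A reader might infer that a definite number of placebo subjects will be misattributed, but the documents give neither the rate of such findings, nor the number entering the extension, nor the share starting on Day 85. A reader might infer that these events are attributed causally to difelikefalin, but the rule only assigns a period; relatedness remains the investigator's judgement and has its own tables. A reader might infer that events are counted in both periods, but the double-blind analysis has a separate SAP that is not available here and may use the complementary rule.

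**Conclusion.** The point holds as a small error in a stated rule. For subjects whose first open-label dose is given at the Day 85 visit, SAP 4.8.1 places findings from that day's pre-dialysis assessments in the open-label AE tables. This departs from Protocol 12.9.1 without being declared in SAP 1.2, and it is inconsistent with the baseline definitions in SAP 4.8.2 and 4.8.3.

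The exposure is concentrated in findings from the single scheduled post-baseline double-blind ECG and full panel, and is 1 in 6 for vital signs and potassium. The conclusion rests on three conditions: a same-day start, which is the default; a finding that is reported as an AE; and an onset date equal to the assessment date. End-of-treatment findings in subjects who start on a later day are not caught. The number of subjects affected cannot be derived, and double counting is only a possibility. Severity: minor.

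**What to change.** In SAP 4.8.1, add a convention limited to AEs dated on the first open-label dosing day:

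- Assign to the double-blind period any AE with an onset time before the dose, or arising from the pre-dialysis assessments.
- Keep events after the dose as open-label.
- Query the site when the time is missing, and default to open-label if the order remains unknown.

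List the change in SAP 1.2 and align it with the double-blind SAP so that each AE is counted in one period only. Do not replace the rule with the protocol's wording alone, because read on dates it loses first-day reactions after the dose.

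The cost is a few lines of SAP text, a small programming change and a few site queries. The default to open-label keeps the present cautious direction for events that cannot be resolved.

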10.4 Assessing AEs

10.4.1 Intensity/Severity

The medical assessment of intensity will be determined by using the following definitions:

Mild: The AE is easily tolerated and does not interfere with usual activity.

Moderate: The AE interferes with daily activity, but the subject is still able to function.

Severe: The AE is incapacitating, and the subject is unable to work or complete usual activity.

Every change in intensity of a particular AE experienced by the subject during the course of the event is recorded.

It is important to note the distinctions between severe AEs and SAEs. Severity is a classification of intensity of a specific event (as in mild, moderate, or severe myocardial infarction); however, the event itself may be of relatively minor medical significance (such

as severe headache). An SAE, however, is an AE that meets any of the regulatory specified criteria required for designation as seriousness described in Section 10.7.1 (i.e., a headache may be severe, interferes significantly with subject's usual function, but would not be classified as serious unless it met 1 of the criteria for SAEs).

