10.5 Recording and Reporting

10.5.1 Persistent or Recurrent AEs

AEs that extend continuously, without resolution, between trial assessments should only be recorded once in the eCRF.

The initial severity of the event should be recorded, and the severity should be updated to reflect the most extreme severity any time the event worsens.

AEs that resolve and subsequently recur should have each recurrence recorded separately in the eCRF.

All AEs persisting at the time of study completion will be followed by the Investigator through contact with the subject until resolution or stabilisation, or the subject is lost to follow-up and cannot be contacted. The outcome must be documented in the subject's source documents.

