10.7.2 SAE Reporting

The SAE reporting period begins at the time the ICF is signed by the subject. The SAE reporting period ends 30 days following the last study visit or until 30 days after last investigational product administration, whichever is longer. After last study visit, SAEs that come to the attention of the Investigator must be reported to the CRO/Sponsor and will be documented in the safety database of the Sponsor only and not in eCRF.

A death occurring during the study or which comes to the attention of the Investigator within 30 days after the last study visit or until 30 days after the last investigational product administration, whichever is longer, whether considered treatment-related or not, must be reported to the Sponsor (or its delegate, e.g., CRO).

Any SAE considered to have a causal relationship (i.e., related) to the investigational product and discovered by the Investigator at any time after the study should be reported. A rationale for the assessment of a causal relationship must be provided by the Investigator. Any safety information that is obtained after database lock of the clinical database will be documented in the safety database and implications for handling the data in the clinical database assessed on an individual case basis.

The occurrence of an SAE must be immediately reported to the Sponsor (or its delegate, e.g., CRO) within 24 hours of awareness by using the study-specific Sponsor SAE form/via SAE CRF/eCRF in the EDC, or as defined in the study monitoring plan. This includes all SAEs (independent of relationship to study treatment).

The onset date of the SAE is defined as the date the signs and symptoms/diagnosis became serious (i.e., met at least 1 of the criteria for seriousness; see Section 10.7.1). If the condition started as a non-serious event and then became serious, 1 AE and 1 SAE will be recorded. The resolution date of the SAE is defined as when the symptoms resolve, or the event is considered chronic (e.g., sequelae) or stable, and/or if the seriousness criteria are no longer applicable.

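### Open-label adverse events are assigned by onset date only, so a non-serious event that starts in the double-blind period and worsens on open-label difelikefalin is missing from every open-label table

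*SAP*

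**What the plan says.** **Assignment to the open-label period.** SAP 4.8.1 gives this rule for the extension: "AEs relative to the open-label extension period are identified as any AE with an onset date on or after the first dose of difelikefalin". The same section adds: "All tabular adverse event summaries will only include AEs relative to the open-label extension period". It has no clause for worsening.

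**Assignment to the double-blind period.** Protocol 12.9.1 also works by onset. For subjects who continue into the extension, its rule reads: "With an onset date after the first dose of the investigational product in the double-blind period up to the first dose of difelikefalin", where the last dose named is the first open-label one.

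**Recording.** Protocol 10.5.1: "AEs that extend continuously, without resolution, between trial assessments should only be recorded once in the eCRF". On that record, "the severity should be updated to reflect the most extreme severity any time the event worsens". A recurrence is different: "AEs that resolve and subsequently recur should have each recurrence recorded separately in the eCRF". Protocol 10.4.1 says: "Every change in intensity of a particular AE experienced by the subject during the course of the event is recorded". It does not say that each change is dated, and no analysis rule uses the changes to assign a period.

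**Becoming serious.** Protocol 10.7.2: "If the condition started as a non-serious event and then became serious, 1 AE and 1 SAE will be recorded". The SAE takes as its onset the date on which it became serious. Protocol 10.5.4 (laboratory findings) and 10.5.6 (vital signs, ECG and other findings) instead update seriousness on the existing record.

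**Carry-over events.** SAP 4.8.1 and Appendix 1 (listing 16.2.7.3) provide one listing of AEs with double-blind onset. It covers those that lead, in the extension, to stopping the drug, leaving the study early or death.

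**The concern.** Safety is a secondary objective (protocol 3.2), and protocol 2.2 gives the collection of more safety data as a reason for the extension. For subjects randomised to placebo, the first open-label dose is their first exposure to difelikefalin. Protocol 2.2 also says that adverse reactions to the drug appear early in treatment. A symptom that was mild on placebo and intensifies after the switch is thus an event that the Placebo/Difelikefalin column ought to show.

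Under an onset-only rule it does not appear there. The special-interest terms in SAP 4.8.1 include dizziness, somnolence and palpitations, which can plausibly be present at a low grade before the switch and then get worse. What is at stake is the descriptive safety profile on first exposure, above all the maximum-severity and special-interest tables.

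**Working it through.** The plan gives no figure to reproduce, because the point rests on definitions. The check follows example records through the rules quoted above.

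**Trace.** Take a Placebo/Difelikefalin subject, with the first open-label dose at day 0. An AE starts at day −5, and the change comes at day +10.

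| Case | eCRF records | Double-blind period | Open-label tables |
|---|---|---|---|
| A. Mild, continuous, becomes severe, never serious | One: onset −5, severe | That record; severe if the update precedes the data cut | Nothing |
| B. Mild, continuous, becomes serious (10.7.2) | Two: AE with onset −5; SAE with onset +10 | The AE, mild | The SAE |
| C. Mild, resolves, recurs as severe | Two: onset −5; onset +10 | Mild AE | Severe AE |
| D. Case A with a worsening rule and severity split by period | One, with an intensity change at +10 | Mild | Severe |

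Only case A goes wrong. Its absence from the open-label tables needs just two rules: one record per continuing event, and onset-only assignment. Display of the worse grade under placebo needs a third, the overwriting of severity, and also depends on when the double-blind data are cut. SAP 2.5.1 places that analysis after all subjects have left the double-blind period, when early switchers may already have been on open-label drug for some time.

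**Direction.** Every AE that meets the onset rule also meets an onset-or-worsening rule, but not the reverse. Open-label counts under the current rule are therefore never higher than under the wider one.

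**Scale per affected subject.** The number of affected subjects is unknown. The protocol plans 129 subjects per group, and entry to the extension is optional. If enrolment meets the plan, a sequence holds at most about 129.
- All 129 enter: 1/129 = 0.78 percentage points per affected subject.
- Assumed sequence of 100: 1/100 = 1.0 point.
- Purely as an assumption, 2 to 5 affected subjects per 100 would remove up to 2 to 5 points. This is an upper bound: a subject counts once per row, so someone with another qualifying open-label AE is already in it.
- Most-common table (2% cut-off in any sequence): 0.02 × 129 = 2.58, so 3 subjects bring a term in; with 100, 0.02 × 100 = 2 subjects. One misassigned subject can decide whether a term is shown.

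**The case against.** **Not every worsening event is lost.** A reader might infer that any AE that worsens on open-label drug vanishes from the tables. The documents do not support that. Becoming serious normally creates an SAE with its own onset date (10.7.2), and a recurrence is a new record (10.5.1). Protocol 9.1 may produce a further AE entry when clinically relevant worsening leads to a change in concomitant treatment. Protocol 10.5.5 has unexpected worsening of the disease under study recorded as an AE. These routes narrow the gap but do not close it. An AE such as dizziness that starts after screening and intensifies without becoming serious, and without a treatment change, has no route. For laboratory, vital-sign and ECG findings, 10.5.4 and 10.5.6 leave even the serious route in doubt.

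**The effect on placebo is not established.** A reader might also infer that the placebo arm's severity profile is inflated. SAP section 1 puts the double-blind analyses in a separate SAP, which may set its own severity rule. The CRF is not available either, so it is unknown whether 10.5.1 (raise to worst) or 10.4.1 (record every change) governs in practice. The effect is possible, not shown.

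**The data are not lost to reporting.** The SAP restricts tables, not listings. Protocol 12.9.1 requires all AEs to be listed with dates, severity and a period flag, and the SAP adds the carry-over listing. This stands, but a listing does not correct an incidence table. The carry-over listing also omits severity increase and drug interruption, although interruption is a row of the SAP's overall summary.

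**The analyses are descriptive.** That is true, and it limits the consequence: no test or primary conclusion is affected. Safety conclusions from the extension still rest on these tables.

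**Conclusion.** The point holds for one class of event: a continuing AE with double-blind onset that worsens in severity after the first open-label dose without becoming serious. Under the written rules it is absent from every open-label AE table. In the Placebo/Difelikefalin sequence the resulting error can only understate AE counts after first exposure. The conclusion assumes that the eCRF follows the single-record rule in 10.5.1.

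The size cannot be derived from the documents. The per-subject figures above show only what one affected subject would do to a row. Whether the open-label grade is also shown under placebo remains conditional on the double-blind SAP and the timing of the data cut. The rule should be corrected because the error runs one way and the correction is cheap. It does not threaten the efficacy conclusions.

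**What to change.** 1. In SAP 4.8.1, define open-label AEs as those with onset, or an increase in intensity, on or after the first open-label dose. Use the intensity changes that protocol 10.4.1 requires to be recorded.
2. Reconcile protocol 10.5.1 with 10.4.1, so that it is clear whether earlier grades are kept or replaced. Reconcile 10.5.4 and 10.5.6 with 10.7.2 on events that become serious.
3. If the eCRF does not date intensity changes, step 1 cannot be programmed as written. In that case, tabulate separately by sequence the AEs ongoing at the first open-label dose, with their worst severity. Also extend the carry-over listing to severity increase and drug interruption.
4. Check the double-blind SAP. If it has no rule on this, its severity tables should use the maximum intensity reached before the first open-label dose.

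**Cost.** Steps 1 and 3 are SAP wording and programming. Step 2 touches protocol text and possibly eCRF instructions, and step 4 lies in another document. Some events will count in both periods, once at onset and once at worsening, which a table footnote can state.
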